#### **4.2.4. Derived Data**

- Age (year)
- Age group (<40, ≥40 years old; <60, ≥60 years old; <65, ≥65 years old)
- Weight group (<60 kg, ≥60 to <100 kg, ≥100 kg)
- BMI ( $\text{kg}/\text{m}^2$ ) =  $\text{Weight (kg)} / ((\text{Height (cm)}) / 100)^2$
- BMI groups (<25  $\text{kg}/\text{m}^2$ , ≥25 to <30  $\text{kg}/\text{m}^2$ , ≥30  $\text{kg}/\text{m}^2$ )
- The duration from onset of AA (year) =  $[(\text{Date of informed consent} - \text{Date of AA onset}) + 1] / 365.25$ .

If year of onset is missing, duration of AA will be set as missing. Otherwise, unknown month will be taken as January, and unknown day will be taken as 01. The duration of AA will be rounded to 1 decimal place before deriving any duration categories.

- The duration from onset of AA (years) category (<5; ≥5 to <10; ≥10 to <15; ≥15 years)
- AA onset age: derived using AA onset date as the reference start date and July 1st of birth year and truncated to a whole-integer age.
- AA onset age category (<18; ≥18 years old)
- Duration of the current episode of AA (year) at baseline =  $[(\text{Date of first dose} - \text{Date of current episode of AA onset}) + 1] / 365.25$ . If a patient is randomized but does not receive

study drug, then the date of randomization is used instead of the first dose date. The duration of current episode of AA will be rounded to 1 decimal place before deriving any duration categories.

- Duration of the current episode of AA at baseline category ( $\geq 0.5$  to  $<1$  ;  $\geq 1$  to  $<2$ ;  $\geq 2$  to  $<4$ ;  $\geq 4$  to  $<8$ ;  $\geq 8$  years)
- Duration of the current episode of AA at baseline category ( $\geq 0.5$  to  $<4$ ;  $\geq 4$  to  $<8$ ;  $\geq 8$  years)
- Duration of the current episode of AA at baseline category ( $<4$ ;  $\geq 4$  years)
- Change from baseline = postbaseline measurement at Visit x – baseline measurement. If a baseline value is missing, it will not be imputed and the change from baseline will not be calculated
- Percent change from baseline at Visit x:  

$$((\text{Post-baseline measurement at Visit x} - \text{Baseline measurement}) / \text{Baseline measurement}) * 100.$$
 If a baseline value is missing, it will not be imputed and percent change from baseline will not be calculated.
- Weight (kg) = weight (lbs) \* 0.454
- Height (cm) = height (in) \* 2.54

### 4.3. Adjustments for Covariates

The randomization to treatment groups at Week 0 (Visit 2) is stratified by duration of current episode at Baseline and geographic region in both phases. Unless otherwise specified, the statistical analysis models will adjust for duration of current episode at Baseline and geographic region. The covariates used in the logistic model for categorical data will additionally include the parameter value at baseline except for endpoints related to SF-36 and HADS. The covariates used in the ANCOVA model for continuous data generally will include the parameter value at Baseline. Inclusion of baseline in the ANCOVA model ensures treatment LSM are estimated at the same baseline value. When a MMRM analysis is performed, baseline value and baseline-by-visit interactions will be included as covariates.

### 4.4. Handling of Dropouts or Missing Data

Depending on the estimand being addressed, different methods will be used to handle missing data as a result of intercurrent events. Intercurrent events can occur through but not limited to the following:

- application of one of the censoring rules (including after permanent study drug discontinuation, after rescue therapy, after dose change, or retreatment)
- discontinuation of inadvertently enrolled patients
- discontinuation from the study due to enrollment in other trials, medical, safety or regulatory reasons, investigator decision, and patient decision
- missing an intermediate visit prior to discontinuation, rescue, dose change, or retreatment
- loss to follow-up.

Non-censor intercurrent events are events that are not due to the application of any censoring rule, i.e., the last four items in the list above.

Note that as efficacy and health outcome data can accrue after a patient permanently discontinues study drug or begins rescue therapy or retreatment, specific censoring rules to the data will be applied to all efficacy and health outcome observations subsequent to these events depending on the estimand being addressed. These specific censoring rules are described below.

*The primary censoring rule* will censor efficacy and health outcome results after permanent study drug discontinuation or results that were collected during remote visits due to the COVID-19 pandemic. Therefore, the data collected remotely will be considered “missing”. This censoring rule will generally be applied to all efficacy and health outcome endpoints and conducted for all defined efficacy analysis populations in the Phase 3 portion except for the Randomized Withdrawal Population (defined in Section 4.2.1).

*A secondary censoring rule* will censor efficacy and health outcome results after permanent study drug discontinuation. This censoring rule will not exclude the data collected during remote visits due to the COVID-19 pandemic and will be applied to selected efficacy and health outcome endpoints conducted for the FAS population (defined in Section 4.2.1). This censoring rule will be applied to uptitration population.

*A tertiary censoring rule* will censor efficacy and health outcome results after permanent study drug discontinuation or after retreatment. This censoring rule will be applied to the Randomized Withdrawal Population (defined in Section 4.2.1).

*A tertiary plus censoring rule* will censor efficacy and health outcome results after permanent study drug discontinuation or after retreatment or results that were collected during remote visits due to the COVID-19 pandemic.

*A quaternary censoring rule* will censor efficacy and health outcome results after permanent study drug discontinuation or after treatment switch. This implies that data will be censored after switching from Baricitinib 1-mg to 4-mg at the Decision Point or after rescue from placebo to Baricitinib at Week 36. This censoring rule will be applied to the Phase 2, Week 36 IAS population (defined in Section 4.2.1).

Table JAHO.4.5 describes the planned imputation methods for selected endpoints, including but not limited to, primary and key secondary efficacy endpoints for Phase 3 portion with associated censoring rules. Sections 4.4.1 through 4.4.6 summarize the imputation methods for the various efficacy and health outcome endpoints.

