a Applicable to all patients at time of screening See EC [9] in protocol for treatments that will require washout.

b The maximal baricitinib dose for patients with renal impairment (defined as eGFR <60 mL/min/1.73 m^2) will be 2-mg QD (see Protocol).

- c At Week 36 patients in the placebo treatment arm who have NOT achieved SALT  $\leq 20$  will be rescued and re-randomized in a 1:1 ratio to baricitinib 2-mg or baricitinib 4-mg. All patients in the baricitinib treatment arms will continue in their current treatment arm regardless of treatment response at Week 36. Patients in the placebo arm who have achieved a SALT  $\leq 20$  will remain on placebo at Week 36. These patients who have experienced spontaneous regrowth on the scalp will remain on placebo for the remainder of the trial, even if relapse is observed later during the study.
- d At Week 52, responders (SALT  $\leq 20$ ) who are eligible (i.e., stayed on the same dose of baricitinib from initial randomization at Visit 2) will be randomized in a 3:1 ratio to either stay on their current dose of baricitinib or transition to placebo (randomized withdrawal).
- e Patients who have been in the baricitinib 4-mg treatment group from Baseline and who have never achieved a SALT  $\leq 20$  by Week 52 AND do not have a  $\geq 2$  point improvement in ClinRO Measure for Eyebrow or Eyelash Hair Loss (nonresponders) at Week 52 will be automatically transitioned to placebo. See footnote “f” for discontinuation criteria at Week 76.
- f Patients who are nonresponders (a SALT  $> 20$ ) at Weeks 52 AND 76 will be automatically discontinued from the study at Week 76, unless they have a  $\geq 2$ -point improvement from baseline in ClinRO Measure for Eyebrow or Eyelash Hair Loss. See Protocol for more details.
- g Responders who experience a loss of treatment benefit after Week 52 ( $> 20$ -point absolute worsening in SALT score) who were randomized to placebo at Week 52 (randomized withdrawal) will be retreated with their baricitinib dose, as randomized at Baseline (Visit 2). Patients who were randomized to remain on baricitinib (randomized withdrawal) will continue to receive the same dose of baricitinib. See Protocol for more details.

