#### **4.2.1.2. Populations for Safety Analysis**

Safety analyses will be conducted using the safety population. Specifically, the safety analysis of Phase 2 portion will use the safety population for the Phase 2 portion whereas the safety analysis of Phase 3 portion will use the safety population for the Phase 3 portion. Safety data will be analyzed for each phase (Phase 2 and Phase 3) by treatment cohort. The treatment cohorts include “as randomized” treatment groups and may include “rescued or switched” to baricitinib 2-mg or 4-mg dose, as appropriate.

For the analysis of safety at the Phase 2 Decision Point interim analysis, data from patients randomized to placebo, baricitinib 1-mg, baricitinib 2-mg, or baricitinib 4-mg and followed up to treatment or dose change or data cut (if no treatment or dose change) of the interim analysis were analyzed.

The safety analysis of the Phase 2, Week 36 interim analysis analyzed safety data up to the data cut-off point, excluding any safety data after the dose change or rescue or beyond Week 52. Refer to [Appendix 2](#) for more details.

At the Phase 3 PO-DBL, the safety data of Phase 3 portion through Week 36 will be analyzed by treatment groups including placebo, baricitinib 2-mg, or baricitinib 4-mg.

At the Week 104 DBL and Week 152 DBL, the safety data will be summarized/analyzed using the Randomized Withdrawal population or the retreated population.

At the F-DBL, the efficacy and safety outcomes will be descriptively summarized using observed data, unless stated otherwise. The safety data will be summarized/analyzed using the safety population unless stated otherwise.

In the rare situation where a patient is Lost to Follow-up at the first postbaseline visit, but some safety data exists (e.g., unscheduled laboratory assessments) after first dose of study drug, a listing of the data or a patient profile will be provided, if requested.

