#### **4.4.2. Modified Last Observation Carried Forward**

For continuous efficacy and health outcome variables, such as SALT percent change from baseline, a modified last observation carried forward (mLOCF) imputation technique replaces missing data with the most recent non-missing post-baseline assessment. The specific modification to the LOCF is data after an intercurrent event will not be carried forward thus the mLOCF is applied after the specified censoring rule is implemented. The mLOCF assumes the effect of treatment remain the same after the event that caused missing data as it was just prior to the missing data event. Analyses using mLOCF require a nonmissing baseline and at least 1 postbaseline measure otherwise the data is missing for analyses purposes. Analyses using mLOCF help ensure the number of randomized patients who were assessed post-baseline is maximized and is reasonable for this indication as very few patients experienced waxing and waning in scalp hair coverage during the course of treatment from the Phase 2 portion; The persistence in treatment effect is also demonstrated in the clinical response seen in other AA studies (Mackay-Wiggan et al. 2016).

For the F-DBL mLOCF will be used as the imputation technique for analysis, as NRI may underestimate the potential treatment effect in a long-term study where patients drop out for multiple reasons.

For efficacy and health outcome analyses, if patients continue with the same dose at Week 52, the mLOCF method described above can be applied without modification. Conversely, for those who change dose at Week 52, mLOCF imputes missing values using the last non-missing assessment after they switch to respective treatment. In the event where there is no assessment done post Week 52 visit, mLOCF method will not be applicable.

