**Table JAHO.4.10 Description of Analyses (F-DBL)**

Measure	Variable	Analysis Method (Section 4.2.3)	Censoring Rule	Population (Section 4.2.1)	Time Point
Severity of Alopecia Tool (SALT)	Proportion of patients achieving SALT $\leq 20$	Descriptive using Obs and mLOCF	Tertiary Censoring Rule	Randomized Withdrawal Population	Weeks 52-200
		Descriptive using Obs and mLOCF	Tertiary Censoring Rule	Uptitration Population	Weeks 52-200
		Descriptive using Obs	Secondary Censoring Rule	Retreated Population	Weeks 52-200

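### At the final lock, the observed-case response rates in the randomized withdrawal drop placebo patients once they are retreated for losing response, and so overstate maintenance on placebo

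*SAP*

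**What the plan says.** **Who is retreated.** SAP 3.1.2, footnote g to the design figure, concerns "Responders who experience a loss of treatment benefit after Week 52", defined there as a SALT worsening of more than 20 points. Those "who were randomized to placebo at Week 52 (randomized withdrawal) will be retreated with their baricitinib dose". For the other arm: "Patients who were randomized to remain on baricitinib (randomized withdrawal) will continue to receive the same dose of baricitinib".

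**What is then removed.** The tertiary rule in SAP 4.4 "will censor efficacy and health outcome results after permanent study drug discontinuation or after retreatment", and "This censoring rule will be applied to the Randomized Withdrawal Population (defined in Section 4.2.1").

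**How the final lock uses it.** In Table JAHO.4.10 the withdrawal row for SALT ≤20 at Weeks 52 to 200 is "Descriptive using Obs and mLOCF" under the tertiary rule. Table JAHO.4.11 has the same method for SALT ≤10, for loss and no loss of benefit, and for SALT change. Tables JAHO.4.12 to 4.15 have it for the PRO and ClinRO responder rows.

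**Which analysis leads.** SAP 4.2.1.2 says: "At the F-DBL, the efficacy and safety outcomes will be descriptively summarized using observed data, unless stated otherwise". SAP 4.4.2 instead names mLOCF as the imputation method for that lock and sets NRI aside. No section ranks the two.

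**The concern.** Retreatment is a consequence of the outcome being measured, and only one arm can have it. A placebo patient who loses benefit counts as a failure at the visit where the loss is seen, is retreated, and has no usable data afterwards. A baricitinib patient with the same loss is not retreated and counts as a failure at every later visit with an observed non-response. No other SAP rule removes baricitinib failures in parallel: the automatic Week 76 discontinuation (SAP 3.1.2, footnote f) requires SALT >20 at Week 52 as well, and these patients were at or below 20 then.

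The Obs placebo rate at a late visit is therefore the rate among patients who had not failed by the visit before. Table JAHO.2.1 lists, as an other secondary objective, the comparison of maintained efficacy between the two withdrawal arms at visits through Week 200. Read as an answer to that objective, the Obs column makes withdrawal look safer for hair retention than it was.

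**Working it through.** **1. Is every retreated patient a failure when censored?** Entry to the withdrawal requires SALT ≤20 at Week 52. SALT is rounded to a whole number (Table JAHO.4.6), so a worsening of more than 20 points from any Week 52 value of 0 to 20 gives at least 0 + 21 = 21. Every patient censored at retreatment is then a SALT ≤20 failure and a loss of benefit.

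**2. Does the censored patient leave the Obs denominator?** The SAP does not define Obs. Table JAHO.4.6 sets SALT ≤20 and SALT ≤10 to missing when the score is missing, and loss or no loss of benefit to missing when either score is missing. Without imputation the patient has no value and drops out.

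**3. Size of the arms.** SAP 4.1 expects about 100 eligible patients. The planning figures are compatible with this: 625 in a 2:2:3 ratio gives about 268 on 4-mg and 179 on 2-mg, and 0.30 × 268 + 0.20 × 179 = 116 responders at the assumed Week 36 rates, so about 14% attrition gives 100. At 3:1 (SAP 3.1.2) that is 75 baricitinib and 25 placebo.

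**4. Illustration.** The documents give no loss rates. Assumptions: constant hazard of loss from Week 52; loss is permanent without retreatment; retreatment starts at the visit where loss is seen; no other dropout. Visits are those in Table JAHO.2.1, where Week 136 precedes Week 152. With L the placebo loss by Week 152 (100 weeks after Week 52):

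- All randomized to placebo: S(152) = 1 − L
- Obs placebo: S(152)/S(136) = (1 − L)^(16/100)
- Patients left in the Obs denominator: 25 × (1 − L)^(84/100)

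The last two columns take baricitinib as 90% maintained (10% loss, also assumed) and show baricitinib minus placebo in points.

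| L | All randomized | Obs | Obs n of 25 | Difference, all kept | Difference, Obs |
|---|---|---|---|---|---|
| 40% | 60% | 92% | 16.3 | 30 | −2 |
| 60% | 40% | 86% | 11.6 | 50 | +4 |
| 80% | 20% | 77% | 6.5 | 70 | +13 |
| 90% | 10% | 69% | 3.6 | 80 | +21 |

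Over placebo loss of 40 to 80% and baricitinib loss of 5 to 20%, the Week 152 difference is 20 to 75 points with all patients kept and −12 to +18 points under Obs.

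**5. The same visit under the SAP's own two methods.** Table JAHO4.9 analyses maintenance of SALT ≤20 over Weeks 52 to 104 with NRI, which counts retreated patients as failures. With L = 80%, Week 104 gives S(104) = 0.2^0.52 = 43% under NRI. The final-lock Obs figure for that visit is 0.2^0.16 = 77% on about 14 patients. (The two tables also treat remote visits differently, which this ignores.)

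**6. What mLOCF does.** SAP 4.4.2 carries forward the last value before the intercurrent event. Taking the value at the retreatment visit as retained, that value is at least 21, so the patient stays in as a SALT failure at every later visit. For SALT change, mLOCF freezes the score at that visit.

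**The case against.** Much can be said for the plan.

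- Every affected row pairs Obs with mLOCF, which already keeps retreated placebo patients as SALT failures.
- Maintenance to Week 104 is covered by NRI. The Kaplan-Meier time to loss of benefit through Week 200 is unaffected, because the event occurs before or at retreatment (on the 20-point definition).
- SAP 4.2.3 makes the final lock descriptive, and the objective is not multiplicity-adjusted. No test or alpha is involved.
- Not every placebo failure leaves. A patient at SALT 15 at Week 52 must exceed 35 to be retreated; at 21 to 35 the patient stays in Obs as a failure. The table above is thus an upper bound on the distortion for SALT ≤20 and ≤10.
- The PRO and ClinRO endpoints in Tables JAHO.4.12 to 4.15 do not themselves trigger retreatment, so the effect there is weaker.
- Obs is undefined. If its denominator were all randomized patients, the problem would not arise.

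All of this limits the scope, and none of it repairs the Obs column. The missing-value rules in Table JAHO.4.6 point to the observed-case reading, and the SAP leaves open whether Obs or mLOCF leads. SAP 4.4.2 sets NRI aside because long-term patients drop out for many reasons; retreatment after loss of benefit is not such a dropout.

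A reader might also infer that mLOCF is itself unfair between arms, since for patients whose dose changed at Week 52 "In the event where there is no assessment done post Week 52 visit, mLOCF method will not be applicable". That touches only patients never assessed after Week 52. A patient retreated for a loss seen at a later visit is not among them, and the documents give no sign that they are many. Carrying Week 52 forward on placebo would count patients never observed off drug as maintained. Requiring a later value in both arms would drop randomized patients. No change is warranted on this ground.

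**Conclusion.** The concern holds for the final-lock Obs response rates in the Randomized Withdrawal Population: directly for SALT ≤20, SALT ≤10 and loss or no loss of benefit in Tables JAHO.4.10 and 4.11, and to a lesser degree for the responder rows in Tables JAHO.4.12 to 4.15. Censoring there is informative and, at loss of benefit, confined to placebo. It favours placebo and understates the benefit of staying on baricitinib. At 60, 80 or 90% placebo loss by Week 152, Obs reads about 86, 77 or 69% against 40, 20 or 10% of all randomized. These sizes rest on assumed loss rates, a constant hazard and the observed-case reading of Obs. Under that model they are exact for loss of benefit.

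A reader might infer that the comparison is reversed. The documents do not support that as a general claim. With 15% baricitinib loss (85% maintained), placebo edges ahead at 60% placebo loss (86%) but not at 80% (77%). Obs usually shrinks the difference; it changes the order only where placebo loss is at the low end of the assumed range or baricitinib loss is at the high end.

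Loss of benefit is also worded in two ways: a worsening of more than 20 points (Table JAHO.2.1; SAP 3.1.2, footnote g) and SALT >20 (Retreated Population, Table JAHO.4.1). Which placebo failures are censored depends on this, and so does the statement that Kaplan-Meier is unaffected.

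**What to change.** Before the final lock, in the SAP:

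1. For the binary withdrawal rows in Tables JAHO.4.10 and 4.11, keep retreated patients in the denominator and count every visit after retreatment as not maintained (or as loss of benefit), as the Week 104 NRI analysis does. Treat the PRO and ClinRO responder rows in Tables JAHO.4.12 to 4.15 the same way, as non-response.
2. Reconcile SAP 4.2.1.2 with 4.4.2 by naming mLOCF, not observed data, as the lead analysis at the final lock. Define Obs and its denominator.
3. For the continuous SALT change rows, where counting as failure does not apply, label Obs as conditional on not having been retreated and show n per arm at each visit.
4. Reconcile the two wordings of loss of benefit.

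The cost is SAP wording and a programming change. No new data are needed, and patient management is not affected by items 1 to 3.

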#### **4.4.1. Nonresponder Imputation**

For the analysis of categorical efficacy and health outcomes variables such as SALT  $\leq$  20 and PRO for Scalp Hair Assessment score of 0 or 1 with a  $\geq$ 2-point improvement from Baseline, the primary imputation method when an intercurrent event occurs will be nonresponder imputation (NRI), which can be justified based on the composite strategy ([ICH 2019]) for handling intercurrent events. This imputation procedure assumes that the effects of treatments disappear

after the occurrence of the intercurrent event. For analyses that utilize any of the censoring methods, randomized patients without at least 1 post-baseline observation will also be defined as nonresponders for all visits. As well, patients who are missing a value prior to discontinuation, rescue, dose change, or retreatment (if censoring on rescue or retreatment), i.e., the patient is missing an intermediate visit, will be imputed as nonresponders on that visit only.

#### **4.4.2. Modified Last Observation Carried Forward**

For continuous efficacy and health outcome variables, such as SALT percent change from baseline, a modified last observation carried forward (mLOCF) imputation technique replaces missing data with the most recent non-missing post-baseline assessment. The specific modification to the LOCF is data after an intercurrent event will not be carried forward thus the mLOCF is applied after the specified censoring rule is implemented. The mLOCF assumes the effect of treatment remain the same after the event that caused missing data as it was just prior to the missing data event. Analyses using mLOCF require a nonmissing baseline and at least 1 postbaseline measure otherwise the data is missing for analyses purposes. Analyses using mLOCF help ensure the number of randomized patients who were assessed post-baseline is maximized and is reasonable for this indication as very few patients experienced waxing and waning in scalp hair coverage during the course of treatment from the Phase 2 portion; The persistence in treatment effect is also demonstrated in the clinical response seen in other AA studies (Mackay-Wiggan et al. 2016).

For the F-DBL mLOCF will be used as the imputation technique for analysis, as NRI may underestimate the potential treatment effect in a long-term study where patients drop out for multiple reasons.

For efficacy and health outcome analyses, if patients continue with the same dose at Week 52, the mLOCF method described above can be applied without modification. Conversely, for those who change dose at Week 52, mLOCF imputes missing values using the last non-missing assessment after they switch to respective treatment. In the event where there is no assessment done post Week 52 visit, mLOCF method will not be applicable.

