### 3.1.2. Study Design

[figure not shown]
The study design includes 5 periods: a 5-week screening period; a 36-week double-blind placebo-controlled treatment period; a 68-week long-term extension period; a 96-week bridging extension; and a posttreatment follow-up period. The Schedule of Activities (SOA) will be the same for patients randomized during Stage 1 and Stage 2, except that some patients randomized during Stage 1 might have one or more unscheduled visits after the Decision Point.

- **Period 1:** Screening period (Visit 1) is between 3 and 35 days prior to Visit 2 (Week 0).
- **Period 2:** 36-week double-blind, placebo-controlled treatment period is from Week 0 (Baseline; Visit 2) to Week 36 (Visit 8).
- **Period 3:** 68-week, long-term extension period with randomized withdrawal (for responders) is from Week 36 (Visit 8) to Week 104 (Visit 18).
- **Period 4:** Bridging extension period is from Week 104 (Visit 18) and up to Week 200 (Visit 24)/Week 248 (Visit 26). Subjects who have completed Week 104 and have not

met criteria of permanent discontinuation will have the possibility to remain in the trial for up to 96/144 additional weeks (up to Week 200/248).

- **Period 5:** posttreatment follow-up period; the posttreatment follow-up visit should occur approximately 4 weeks after the last dose of investigational product (IP). Patients who have completed Week 200/248 and who will continue on marketed product beyond Week 200 do not need to complete Period 5 (Visit 801).

Note: Patients who have discontinued IP and remain in the study for more than 28 day without IP will have an Early Termination Visit (ETV); however, a separate follow-up visit (V801) is not required. [Figure JAHO.3.2](#) illustrates the study design. The full visit schedule is outlined in the protocol.

Abbreviations: ClinRO = clinician-reported outcome; EC = exclusion criterion; eGFR = estimated glomerular filtration rate; ET = early termination; IP = investigational product; PBO = placebo; PTFU = posttreatment follow-up; QD = once daily administration; RW = randomized withdrawal 1; SALT = Severity of Alopecia Tool; V = Visit.

Note: Subjects who have completed Week 104 in the Long-term extension and have not met criteria of permanent discontinuation will have the possibility to remain in the trial for up to 96/144 additional weeks (up to Week 200/248) and have similar follow-up procedures.

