Patients who achieve a SALT  $\leq 20$  at Week 52 (responders) AND who have remained on the same dose of baricitinib from randomization (Visit 2) to Week 52, will enter the randomized withdrawal, which is meant to evaluate the change in clinical response after treatment withdrawal, and does not account for whether the sample size is sufficient to detect statistical difference between baricitinib and placebo. It is expected that there would be approximately 100 patients eligible for the randomized withdrawal.

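### In the final-lock mLOCF rows for the Randomized Withdrawal Population, a responder who stops study drug counts as maintained to Week 200, and no planned responder analysis counts stopping as failure.

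*SAP*

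**What the plan says.** The point concerns the long-term analyses of the main study at the final lock (F-DBL). The protocol addendum's own 20-patient, 52-week analysis uses observed cases and is not affected.

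- **The method at the final lock.** SAP 4.4.2 states: "For the F-DBL mLOCF will be used as the imputation technique for analysis, as NRI may underestimate the potential treatment effect".
- **Data after stopping exist.** SAP 4.4 notes that "efficacy and health outcome data can accrue after a patient permanently discontinues study drug".
- **They are removed.** The tertiary rule, assigned to the Randomized Withdrawal Population, "will censor efficacy and health outcome results after permanent study drug discontinuation or after retreatment". The secondary rule also removes results after permanent discontinuation.
- **The gap is then filled.** SAP 4.4.2 says that "data after an intercurrent event will not be carried forward thus the mLOCF is applied after the specified censoring rule is implemented". It gives the assumption as: "The mLOCF assumes the effect of treatment remain the same after the event that caused missing data as it was just prior".
- **The rule is used for responder proportions.** Tables JAHO.4.10 to 4.15 list observed data and mLOCF together, over Weeks 52 to 200, for ten responder endpoints in the Randomized Withdrawal Population: SALT ≤20, SALT ≤10, with and without loss of benefit, three eye-related PRO responses, the scalp PRO response, and the two ClinRO responses. Several of these also have Uptitration rows. Retreated Population responder rows use observed data only.
- **Week 104 was different.** Table JAHO4.9 lists maintained SALT ≤20 in the Randomized Withdrawal Population with NRI, under the tertiary plus censoring rule.

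**The concern.** Table JAHO.2.1 sets the objective as maintenance of response at successive visits to Week 200. Everyone who enters randomized withdrawal is a SALT ≤20 responder at Week 52, so a patient who stops drug early will usually have a response to carry. The resulting figure describes status at the last on-drug assessment but is reported under the Week 200 label.

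The clinical argument in SAP 4.4.2 is mainly about patients on treatment: "very few patients experienced waxing and waning in scalp hair coverage during the course of treatment". Here the rule is applied after treatment has ended. The randomized withdrawal itself is "meant to evaluate the change in clinical response after treatment withdrawal", and the design provides for retreatment after loss of benefit, so the trial expects that response can be lost off drug. The stated reason for leaving NRI is that it may underestimate the effect. The SAP does not discuss overestimation by mLOCF.

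What is at stake is the long-term maintenance rate. It would barely respond to how many responders stop drug.

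**Working it through.** **No plan figure to reproduce.** The SAP gives no expected maintenance rate, long-term discontinuation rate or off-drug relapse rate. It expects about 100 patients in randomized withdrawal at 3:1, so about 75 stay on baricitinib and 25 go to placebo.

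**Step 1: how each method counts a stopper.** Let S be the share who stop before Week 200, m the maintained share among those still on drug, and c the share of stoppers who were responders at their last on-drug visit.

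- mLOCF = (1 − S)m + Sc
- Observed = m
- NRI = (1 − S)m
- mLOCF − NRI = Sc

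With m = 0.90 and c = 1 (assumed):

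| S | mLOCF | Observed | NRI | If half of stoppers relapse and this is counted |
|---|---|---|---|---|
| 10% | 91% | 90% | 81% | 86% |
| 20% | 92% | 90% | 72% | 82% |
| 30% | 93% | 90% | 63% | 78% |

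If c = m = 0.90, mLOCF stays at 90% for every S. So mLOCF does not fall as patients stop, provided that stoppers are at least as often responders as stayers. The observed-data figure does not move either.

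**Step 2: size in the baricitinib arm over Weeks 52 to 200.** T = 148/52.18 = 2.84 years. All three rates are assumptions:

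- on-drug loss of 10% over the window: λ = −ln(0.90)/T = 0.0371 per year
- discontinuation δ = 0.05, 0.10 or 0.15 per year
- off-drug loss of 20%, 50% or 80% per year: η = −ln(0.80), −ln(0.50) or −ln(0.20) = 0.223, 0.693 or 1.609

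Formulas:

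- NRI = exp(−(λ+δ)T)
- mLOCF = NRI + [δ/(λ+δ)] × [1 − exp(−(λ+δ)T)]
- Expected actual status = NRI + δ·exp(−ηT) × [1 − exp(−(λ+δ−η)T)]/(λ+δ−η)

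Example with δ = 0.10 and 80% off-drug loss: NRI = exp(−0.389) = 0.678; mLOCF = 0.678 + 0.729 × 0.322 = 0.913; actual status = 0.678 + 0.045 = 0.723.

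| δ per year | mLOCF | Observed | NRI | Actual status at 20 / 50 / 80% off-drug loss |
|---|---|---|---|---|
| 0.05 | 90.7% | 90.0% | 78.1% | 87.3 / 83.4 / 80.6% |
| 0.10 | 91.3% | 90.0% | 67.8% | 84.8 / 77.4 / 72.3% |
| 0.15 | 91.8% | 90.0% | 58.8% | 82.6 / 72.1 / 64.9% |

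Errors in points, from unrounded values:

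| δ per year | mLOCF minus actual (20 / 50 / 80%) | NRI minus actual (20 / 50 / 80%) |
|---|---|---|
| 0.05 | +3.4 / +7.3 / +10.0 | −9.2 / −5.3 / −2.5 |
| 0.10 | +6.4 / +13.8 / +19.0 | −17.1 / −9.7 / −4.5 |
| 0.15 | +9.2 / +19.7 / +26.9 | −23.8 / −13.3 / −6.1 |

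**Step 3: is a stopper a failure anywhere at the final lock?** In the mLOCF rows the stopper keeps the last on-drug status. In the observed-data rows the same censoring takes the stopper out of numerator and denominator. In the Kaplan-Meier time to loss of benefit (Table JAHO.4.11) the stopper is censored under the tertiary rule. The answer is no.

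**The case against.** The case for leaving the plan alone has real force.

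- **The analyses are descriptive.** SAP 4.2.3 plans no inferential tests at the final lock unless otherwise stated, so no error rate is affected. SAP 4.2.1.2 makes observed data the default, and each affected row has an observed-data version. This stands, but it does not close the gap shown in Step 3.
- **The SAP offers more support than on-treatment stability.** It also cites persistence of effect in other alopecia areata studies and says that long-term dropout has several causes. That argues against NRI as the only method. It does not show that response persists after this drug is stopped.
- **NRI discards the same off-drug data.** It scores kept hair as failure, and with slow off-drug loss its error exceeds that of mLOCF. This stands, and it rules out simply swapping one method for the other.
- **The model treats stopping as unrelated to response.** Where patients stop because response was lost, the two methods agree. This would narrow the gap.

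Stronger readings that a reader might infer are not supported:

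- *All relapse is hidden.* Relapse seen on drug is carried as failure. A placebo patient retreated after worsening is censored only after retreatment, so the carried value is normally the loss. Patients who change dose at Week 52 and have no later assessment are not carried.
- *Uptitration response is broadly overstated.* These patients start with SALT >20. The design discontinues those still above 20 at Week 76 unless eyebrow or eyelash hair has improved, so they carry nonresponse. Only patients who responded after Week 52 and then stopped are affected.
- *Any difference from the Week 104 lock comes from imputation alone.* The censoring rule changed too: tertiary plus removes remote-visit data. Some Week 104 rows also use multiple imputation with NRI.
- *Week 104 completers are carried another 96 weeks.* SAP 3.1.2 says only that patients "will have the possibility to remain in the trial for up to 96/144 additional weeks". The SAP does not say how mLOCF treats those who decline.

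**Conclusion.** The point holds for the mLOCF rows of the Randomized Withdrawal responder proportions, and in a limited way for Uptitration. By construction, those rows cannot show relapse after study drug is stopped, and neither companion analysis counts stopping as failure. The same population had an NRI figure for maintained SALT ≤20 at Week 104.

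The direction follows from the SAP text, provided that some stoppers were responders when they stopped and some of those later relapse. The size is not known from the documents. Under the assumptions in Step 2, mLOCF is too high by about 3 to 27 points and NRI too low by about 2.5 to 24 points at Week 200. Neither method is right alone; shown together they bracket the answer in this model. The change should be made, but it does not threaten the primary analysis, and the evidence does not support removing mLOCF.

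**What to change.** In SAP 4.4.2 and Tables JAHO.4.10 to 4.15:

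1. For each Randomized Withdrawal responder row now planned with observed data and mLOCF, add an NRI row under the same tertiary censoring rule that scores visits after permanent discontinuation as nonresponse. Show it beside the mLOCF row.
2. Head the mLOCF row *response at last on-treatment visit*.
3. Report the number of patients with observed on-drug data at each visit, so that readers can see how much of each later rate is carried forward.

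The cost is SAP wording and one more programmed row for each of the ten endpoints. The companion figure will look less favourable and is conservative for stoppers who keep their hair; the mLOCF row beside it shows the other bound.
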